Participants (males and females 18 to 49 years of age, inclusive), will be included in the study if they are in good health as determined by medical history, clinical laboratory assessments, vital sign measurements, a physical examination at screening and per investigator judgement. Negative pregnancy tests will be required at screening and before vaccine administration for female participants of childbearing potential. Flavivirus serostatus (positive or negative) will be determined by ELISA or other commercially available serological assay. The full lists of inclusion and exclusion criteria are provided in Section 3.2.1 and Section 3.2.2, respectively.

Safety Assessments:

Safety assessments will include monitoring and recording of solicited AEs (local and systemic reactogenicity events) and unsolicited AEs, serious AEs (SAEs), AEs of special interest (AESIs), AEs leading to study withdrawal, medically attended AEs (MAAEs); clinical laboratory test results (hematology, serum chemistry, and coagulation); vital sign measurements; and physical examination findings.

Immunogenicity Assessments:

Immunogenicity assessments will include the following:

- Serum neutralizing antibodies (nAb) against ZIKV
- Serum binding antibodies (bAb) against ZIKV

Vaccine, Dosage, and Route of Administration:

mRNA-1893 is a novel lipid nanoparticle (LNP)-encapsulated mRNA-based vaccine encoding the full pre-membrane and envelope (prME) structural polyproteins of ZIKV. mRNA-1893 consists of an mRNA Drug Substance formulated with LNPs. mRNA-1893 is provided as a sterile liquid for injection at a concentration of 0.5 mg/mL in 100 mM Tris buffer, 7% propylene glycol, and 1 mM diethylenetriamine-pentaacetic acid (DTPA).

mRNA-1893 (10, 30, 100, or 250 µg) and placebo will be prepared as outlined in the pharmacy manual and administered via IM injection (0.5 mL) into the deltoid muscle on designated vaccination days. The second dose of vaccine or placebo will be administered preferably in the same arm used for the first dose.

The placebo is 0.9% sodium chloride injection, United States Pharmacopeia (USP) or British Pharmacopeia (BP).

Sample Size:

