3.2.1 Inclusion Criteria

Each participant must meet all of the following criteria during the Screening Phase and at Day 1, unless noted otherwise, to be enrolled in this study:

- 1. Male or female 18 to 49 years of age, inclusive.
- 2. Understands and agrees to comply with the study procedures and provides written informed consent.
- 3. In the opinion of the investigator, can and will comply with the requirements of the protocol (e.g., complete diary cards, return for follow-up visits, be available for safety telephone calls).
- 4. Is in good general health, as determined by medical history, clinical laboratory assessments, vital sign measurements, and physical examination at screening.
- 5. For flavivirus-seropositive group, has positive flavivirus test results (including dengue, West Nile, and Zika) as determined by ELISA or other commercially available serological assay.
- 6. For flavivirus-seronegative group, has negative flavivirus test results (including dengue, West Nile, and Zika) as determined by ELISA or other commercially available serological assay.
- 7. Female participants of childbearing potential may be enrolled in the study, if the participant: (1) has a negative urine pregnancy test at Screening, Day 1, and before second vaccine administration, (2) has practiced adequate contraception (Glossary of Terms) or is abstaining from all activities that could lead to pregnancy for 30 days before the first vaccination, and (3) has agreed to continue adequate contraception through 3 months after the last vaccination.
- 8. Female participants of nonchildbearing potential may be enrolled in the study. Nonchildbearing potential is defined as bilateral tubal ligation > 1 year before screening, bilateral oophorectomy, hysterectomy, or menopause (Glossary of Terms). The

follicle-stimulating hormone level may be measured at the discretion of the investigator to confirm menopausal status.

9. Male participants must agree to practice adequate contraception (Glossary of Terms) from the time of the first vaccination and through 3 months after the last vaccination. Males must also agree to refrain from donation of sperm from the time of first vaccination until 3 months following the last vaccination.

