4.2 Secondary Endpoints

The secondary endpoints for the study are the following:

• Geometric mean titer (GMT) of neutralizing antibody (nAb) against ZIKV at Day 1, Day 29, Day 57, Month 7, and Month 13 as measured by PRNT

Protocol mRNA-1893-P101

• GMT of nAb in initially seronegative participants against ZIKV at Day 1, Day 29, Day 57, Month 7, and Month 13 as measured by PRNT

- GMT of nAb in initially seropositive participants against ZIKV at Day 1, Day 29, Day 57, Month 7, and Month 13 as measured by PRNT
- Percentage of participants who seroconverted from Day 1 (baseline) to Day 29, from Day 1 to Day 57, from Day 1 to Month 7, and from Day 1 to Month 13. A seroconversion is defined as a change of PRNT from below the lower limit of quantification (LLOQ) to a PRNT equal to or above LLOQ, or an increase of at least 4-foldin participants with pre-existing PRNT titers.
- Proportion of initially seronegative participants with a seroresponse at Day 29, Day 57, Month 7, and Month 13 as measured by PRNT. A seroresponse is defined as a change of PRNT from below the LLOQ to greater than or equal to the LLOQ.
- Proportion of initially seropositive participants with a 2-fold or 4-fold increase in nAb titers as compared with baseline as measured by PRNT

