5.3 Randomization

Participants will be randomly assigned (Day 1) in a blinded manner using the centralized Interactive Response Technology (IRT), with approximately 30 participants assigned to each cohort. Study vaccine dosing will begin with Cohort 1 (10 µg mRNA-1893 or placebo), followed sequentially by Cohort 2 (30 µg mRNA-1893 or placebo), Cohort 3 (100 µg mRNA-1893 or placebo), and Cohort 4 (250 µg mRNA-1893 or placebo). Within each cohort, participants will be randomly assigned in a blinded manner to receive either mRNA-1893 vaccine or placebo (4:1 mRNA-1893 vaccine to placebo) using the centralized IRT. Participants will be stratified according to flavivirus baseline serostatus.

In each cohort, the initial 5 participants (all seronegative) will be randomly assigned to vaccine or placebo (4:1 mRNA-1893 vaccine to placebo) before the remaining participants (n=25, 20 seronegative and 5 seropositive) are enrolled in the cohort.

Randomization by the centralized IRT will be in accordance with pre-generated randomization schedules, with only the unblinded pharmacy personnel having controlled access.

Dose group assignment in each cohort and stratification within each cohort is summarized in Table 1.

Protocol mRNA-1893-P101

Table 1: Dose Group Assignment

| | Dose Group | | | eus Status Tication ^a | Total | | |
|--------|------------|-----------|-----------|-------------------------------------|---------|--|--|
| Cohort | Assignment | n | Status | n | (Ratio) | | |
| | mRNA-1893 | 24 | + | 4 | | | |
| 1 | 10 μg | 24 | - | 20 | 30 | | |
| 1 | Placebo | 6 | + | 1 | (4:1) | | |
| | Placebo | 0 | - | 5 | | | |
| | mRNA-1893 | 24 | + | 4 | | | |
| 2 | 30 μg | 24 | - | 20 | 30 | | |
| 2 | Placebo 6 | 6 | + | 1 | (4:1) | | |
| | | riacedo 6 | - | 5 | | | |
| | mRNA-1893 | 24 | + | 4 | | | |
| 3 | 100 μg | 24 | - | 20 | 30 | | |
| 3 | Dlasaka | 6 | + | 1 | (4:1) | | |
| | Placebo | 6 | - | 5 | | | |
| | mRNA-1893 | 24 | + | 4 | | | |
| 4 | 250 μg | 24 | - | 20 | 30 | | |
| 4 | DI 1 | - | + | 1 | (4:1) | | |
| | Placebo | 6 | - | 5 |] | | |
| | | | Total 120 | | | | |

Abbreviations: - = flavivirus seronegative; + = flavivirus seropositive.

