7.1 General Considerations

Participants will be identified in the listings by the participant identification number concatenated with the site number. For rescreened participants, only the data collected from the last screening will be presented in the data listings and included in the summaries.

Data from participants excluded from an analysis set will be presented in the data listings but not included in the calculation of summary statistics for the corresponding analysis set.

Although date of physical exam is collected in the eCRF, this data will not be presented in the data listings.

The following treatment groups will be used for summary purposes:

- Placebo
- mRNA-1893 10 μg
- mRNA-1893 30 μg
- mRNA-1893 100 μg
- mRNA-1893 250 μg
- mRNA-1893 Total

For categorical variables, frequencies and percentages will be presented. Continuous variables will be summarized using descriptive statistics (number of participants, mean, median, standard deviation [SD], minimum, and maximum). See Appendix B for variable display standards.

When count data are presented, the percentage will be suppressed when the count is zero in order to draw attention to the non-zero counts. A row denoted "Missing" will be included in count tabulations where specified on the shells to account for dropouts and missing values. The denominator for all percentages will be the number of participants in that treatment within the analysis set of interest, unless otherwise specified.

For the change from Baseline safety summaries, Baseline will be defined as the last non-missing measurement (including repeated and unscheduled assessments) before the first vaccination.

For the immunogenicity analyses, Baseline will be defined as the last non-missing assessment collected at Visit Day 1.

Study Day relative to the first vaccination will be calculated as below:

- Study Day prior to the first vaccination will be calculated as: date of assessment/event date of the first vaccination;
- Study Day on or after the date of the first vaccination will be calculated as: date of assessment/event date of the first vaccination + 1;

Study Day relative to the most recent vaccination will be calculated as below:

- Study Day prior to the first vaccination will be calculated as: date of assessment/event date of the first vaccination;

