7.7.2 Analysis of nAb against ZIKV by PRNT

The nAb against ZIKV by PRNT will be summarized by treatment group and scheduled visit as follows:

• GMT of nAb against ZIKV at Day 1, Day 29, Day 57, Month 7, and Month 13 as measured by PRNT with corresponding 95% CIs.

Protocol mRNA-1893-P101

• GMT of nAb against ZIKV in initially flavivirus seronegative participants at Day 1, Day 29, Day 57, Month 7, and Month 13 as measured by PRNT with corresponding 95% CIs.

- GMT of nAb against ZIKV in initially flavivirus seropositive participants at Day 1, Day 29, Day 57, Month 7, and Month 13 as measured by PRNT with corresponding 95% CIs.
- Percentage of participants who seroconverted from Day 1 (baseline) to Day 29, from Day 1 to Day 57, from Day 1 to Month 7, and from Day 1 to Month 13.
- Proportion of initially seronegative participants with a seroresponse at Day 29, Day 57, Month 7, and Month 13 as measured by PRNT.
- Proportion of initially seropositive participants with a 2-fold or 4-fold increase in nAb titers as compared with baseline at Day 29, Day 57, Month 7, and Month 13 as measured by PRNT.
- Reverse cumulative distribution of nAb against ZIKV at Day 1, Day 29, Day 57, Month 7, and Month 13 as measured by PRNT.

7.7.3 Analysis of nAb against ZIKV by Microneutralization Assay and Reporter Virus Neutralization Test

The nAb against ZIKV as measured by MN and RVNT will be summarized by treatment group and scheduled visit as follows:

- GMT of nAb against ZIKV at Day 1, Day 29, Day 57, Month 7, and Month 13 as measured by MN and RVNT with corresponding 95% CIs.
- GMT of nAb against ZIKV in initially flavivirus seronegative participants at Day 1, Day 29, Day 57, Month 7, and Month 13 as measured by MN and RVNT with corresponding 95% CIs.
- GMT of nAb against ZIKV in initially flavivirus seropositive participants at Day 1, Day 29, Day 57, Month 7, and Month 13 as measured by MN and RVNT with corresponding 95% CIs.
- Percentage of participants who seroconverted from Day 1 (baseline) to Day 29, from Day 1 to Day 57, from Day 1 to Month 7, and from Day 1 to Month 13.
- Proportion of initially seronegative participants with a seroresponse at Day 29, Day 57, Month 7, and Month 13 as measured by MN and RVNT.

Proportion of initially seropositive participants with a 2-fold or 4-fold increase in nAb titers as compared with baseline at Day 29, Day 57, Month 7, and Month 13 as measured by MN and RVNT.

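### Seroresponse is counted in a group set by screening serology but scored on baseline Zika titre, and no responder measure is planned in common for the two serostatus strata

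*SAP*

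**What the plan says.** **How serostatus is set.** The Protocol Synopsis (Study Population) states: "Flavivirus serostatus (positive or negative) will be determined by ELISA or other commercially available serological assay". Protocol 3.2.1 applies this to each group. Criterion 5 admits to the seropositive group a participant who "has positive flavivirus test results (including dengue, West Nile, and Zika) as determined by ELISA or other commercially available serological assay". Criterion 6 reads: "For flavivirus-seronegative group, has negative flavivirus test results (including dengue, West Nile, and Zika) as determined by ELISA or other commercially available serological assay". Neither criterion requires a PRNT result. SAP 5.3 uses the same factor in the randomization: "Participants will be stratified according to flavivirus baseline serostatus".

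**How response is scored.** SAP 4.2 gives three PRNT responder measures:

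- Seroresponse, for initially seronegative participants: "A seroresponse is defined as a change of PRNT from below the LLOQ to greater than or equal to the LLOQ".
- Fold rise, for the other stratum: "Proportion of initially seropositive participants with a 2-fold or 4-fold increase in nAb titers as compared with baseline as measured by PRNT".
- Seroconversion, for all participants: either crossing the LLOQ or at least a 4-fold rise from a pre-existing titre.

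SAP 4.3 repeats the single-route seroresponse definition for the additional neutralization assays. It gives no definition of seroresponse for binding antibody.

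**How the results are tabulated.** SAP 7.7.2 summarizes PRNT by treatment group and visit. GMTs are also split by flavivirus serostatus, but the seroconversion row ("Percentage of participants who seroconverted from Day 1 (baseline) to Day 29", and likewise for later visits) is not. SAP 7.7.3 and 7.7.4 follow the same pattern. On denominators, SAP 7.1 says: "The denominator for all percentages will be the number of participants in that treatment within the analysis set of interest, unless otherwise specified".

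**The concern.** Membership of the seronegative group comes from one test, a flavivirus serology up to 28 days before Day 1. The responder event comes from another, a Zika neutralization titre measured against Day 1. Nothing guarantees that the two agree. Where a seronegative participant already has a measurable Day 1 titre, the seroresponse definition has no route for that person, and no rule removes the person from the count.

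Protocol 1.4 states that immune responses will be compared between the strata, and Protocol 3.6.8 says the interim results inform dose selection. As planned, seronegatives get a threshold-crossing rate and seropositives get fold-rise rates. The one measure that could be applied to both is reported only for the strata combined. Planned tables would not let a reader set one stratum's responder rate beside the other's on the same definition.

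**Working it through.** **The plan's own figures.** The documents state no figure for the responder endpoints. The only design calculation (SAP 5.2) is the chance of at least one AE among 24 vaccinees per dose. It reproduces: 1 − 0.90^24 = 0.920 and 1 − 0.95^24 = 0.708. It has no bearing on this point.

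**Step 1: which assay defines *initially seronegative*?** The responder bullets do not say. Four places point to screening serology:

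- The Protocol Synopsis and 3.2.1 define serostatus only that way.
- SAP 5.3 stratifies on it.
- SAP 7.2.2 presents demographics by serostatus at screening.
- SAP 7.7.2 names the matching GMT group as flavivirus seronegative and plans a Day 1 GMT for it. If the group were defined by PRNT below LLOQ, that Day 1 GMT would always equal 0.5 × LLOQ under the substitution in SAP 7.1, and the row would carry no information.

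**Step 2: routes to response, by baseline.** In the seronegative stratum:

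| Day 1 titre | Seroresponse | Seroconversion |
|---|---|---|
| Below LLOQ | Reach LLOQ | Reach LLOQ |
| At or above LLOQ | None | At least 4-fold rise |

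SAP 7.1 keeps the second row in the denominator, because nothing in SAP 4.2, 4.3 or 7.7 specifies otherwise.

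**Step 3: size.** SAP Table 1 assigns 20 seronegative vaccinees per dose, 80 over four doses. With d discordant participants, the ceiling is (20 − d)/20, so each one costs 1/20 = 5 points in a dose group and 1/80 = 1.25 points over all doses. The table assumes that all others respond and that the full stratum is in the per-protocol set. Intervals are Clopper-Pearson, the SAP's method.

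| d | As written | Denominator limited to baseline below LLOQ |
|---|---|---|
| 0 | 20/20 = 100% (83.2–100) | 20/20 = 100% (83.2–100) |
| 1 | 19/20 = 95% (75.1–99.9) | 19/19 = 100% (82.4–100) |
| 2 | 18/20 = 90% (68.3–98.8) | 18/18 = 100% (81.5–100) |

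**Step 4: how likely is d ≥ 1?** The documents give no rate. For an assumed rate q, the chance of at least one in a dose group of 20 is 1 − (1 − q)^20:

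| Assumed q | Chance of at least one in 20 |
|---|---|
| 0% | 0% |
| 1% | 18% |
| 5% | 64% |
| 10% | 88% |

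**Step 5: fold rise from below LLOQ.** A flavivirus-seropositive participant may have no measurable Zika titre on Day 1. If 0.5 × LLOQ were used as the baseline, reaching LLOQ gives LLOQ/(0.5 × LLOQ) = 2-fold, and 4-fold needs 2 × LLOQ. SAP 7.1 and Protocol 3.6.7 state that substitution for GMTs only, so the fold-rise endpoint has no rule here.

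**The case against.** The strongest reply is that the screening reading is inferred. The seroresponse bullet in SAP 7.7.2 omits the word flavivirus and ends with PRNT, and the definition itself starts below the LLOQ. If the group was meant to be PRNT-negative at baseline, nobody is structurally excluded from responding. This stands as a caveat, but the places listed in step 1 favour screening serology, and if PRNT was meant the SAP needs to say so.

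Discordance may also be rare. Seronegatives must test negative for dengue, West Nile and Zika, and Protocol 3.2.2 excludes anyone ever vaccinated against several flaviviruses. That stands too: the documents do not support a statement that the reported rates will be too low.

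Much is visible elsewhere. Day 1 GMTs by stratum, Day 1 reverse cumulative distributions, full listings and overall seroconversion are all planned, and stratum GMTs already give a common continuous measure. This limits the consequence, but it does not supply a responder rate by stratum. With 4 seropositive vaccinees per dose such a rate will be imprecise in any case (4/4 has a 95% interval of 39.8–100%).

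A reader might go further and infer that crediting a seropositive participant for merely reaching the LLOQ is an error. That does not hold, because seroconversion credits the same event. A reader might also infer that each such participant shifts the seropositive 2-fold rate by 25 points (1/4). That follows only if 0.5 × LLOQ is used for fold rise, which the documents do not say.

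**Conclusion.** The point holds as a modest defect in descriptive secondary and exploratory endpoints. On the best-supported reading of serostatus, a seronegative participant with a Day 1 neutralization titre at or above LLOQ is counted but cannot be a seroresponder, by PRNT, MN or RVNT. The cost is 5 points off the attainable rate per such participant in a dose group of 20. Whether any will occur is unknown: with 0 to 2 of 20, the ceiling runs from 100% to 90%.

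Independently of the discordance rate, the plan gives the two strata no shared responder measure for a comparison the protocol announces. The missing rule for fold rise from below LLOQ is a separate gap, whose effect cannot be sized until the rule is stated. No primary endpoint or formal test is affected.

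**What to change.** In the SAP:

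1. State that *initially seronegative* and *initially seropositive* mean screening serostatus.
2. In 7.7.2 to 7.7.4, report seroconversion with Clopper-Pearson intervals within each serostatus stratum as well as overall.
3. Restrict the PRNT, MN and RVNT seroresponse denominators to participants with baseline below that assay's LLOQ.
4. Show, by stratum and treatment group, how many have baseline below and how many at or above LLOQ.
5. State how fold rise is computed when baseline is below LLOQ.

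This needs no new data and only a few table rows. The seroresponse denominator may shrink slightly. Because item 3 alters the population of a protocol secondary endpoint, the change belongs in SAP Section 8.

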4.3 Exploratory Endpoints

The exploratory endpoints for the study include the following:

- GMT of nAb against ZIKV at Day 1, Day 29, Day 57, Month 7, and Month 13 as measured by additional neutralization assay
- GMT of nAb in initially seronegative participants against ZIKV at Day 1, Day 29, Day 57, Month 7, and Month 13 as measured by additional neutralization assay
- GMT of nAb in initially seropositive participants against ZIKV at Day 1, Day 29, Day 57, Month 7, and Month 13 as measured by additional neutralization assay
- Percentage of participants who seroconverted from Day 1 (baseline) to Day 29, from Day 1 to Day 57, from Day 1 to Month 7, and from Day 1 to Month 13. A seroconversion is defined as a change of nAb titer (by additional neutralization assay) from below the LLOQ to a titer equal to or above LLOQ, or a multiplication by at least 4 in participants with pre-existing nAb titer as measured by additional neutralization assay
- Proportion of initially seronegative participants with a seroresponse at Day 29,
 Day 57, Month 7, and Month 13 as measured by additional neutralization assay. A

seroresponse is defined as a change of titer from below the LLOQ to greater than or equal to the LLOO.

- Proportion of initially seropositive participants with a 2-fold or 4-fold increase in nAb titers as compared with baseline as measured by additional neutralization assay
- GMC of serum binding antibodies (bAb) against ZIKV at Day 1, Day 29, Day 57, Month 7, and Month 13 as measured by ELISA binding assay
- GMC of bAb in initially seronegative participants against ZIKV at Day 1, Day 29, Day 57, Month 7, and Month 13 as measured by ELISA binding assay
- GMC of bAb in initially seropositive participants against ZIKV at Day 1, Day 29, Day 57, Month 7, and Month 13 as measured by ELISA binding assay
- Percentage of participants who seroconverted from Day 1 (baseline) to Day 29, from Day 1 to Day 57, from Day 1 to Month 7, and from Day 1 to Month 13. A seroconversion is defined as a change of bAb concentration from below the LLOO to a titer equal to or above the LLOQ, or a multiplication by at least 4 in participants with pre-existing bAb concentration as measured by ELISA binding assay
- Proportion of initially seronegative participants with a seroresponse at Day 29, Day 57, Month 7, and Month 13 as measured by ELISA binding assay
- Proportion of initially seropositive participants with a 2-fold or 4-fold increase in bAb concentration as compared with baseline as measured by ELISA binding assay
- Immunoglobulin G (IgG) and immunoglobulin M (IgM) antibodies against envelope- and NS1- based antigens present in serum collected at baseline and at end of study measured as antibody binding by ELISA or equivalent methodology to flaviviruses

Study Design

